4.10.1 ER and PgR

ER and PgR expression will be determined by the percentage of positively stained tumour nuclei in each staining category, i.e., negative ‘-/-’, weak ‘+’, moderate ‘++’, strong ‘+++’. The sum of the

percentages of these 4 staining categories will be 100%. Then, ER and PgR expression will be assessed using the following manual H-score method, which yields to a manual H-score range of 0 to 300.

$$\text{H-score} = (1 * \% \text{ of } +) + (2 * \% \text{ of } ++) + (3 * \% \text{ of } +++).$$

When a biopsy contains only 0-100 tumour cells, then H-score is not reported and not evaluable (NE) will be stated.

The primary and secondary pharmacodynamic biomarker variables of percentage change from baseline in ER and PgR expressions after 5 to 7 days of AZD9833 treatment for Stage 1 and Stage 2; and after 12 to 15 days of AZD9833 treatment for Stage 3 will be listed and summarised based on the PD analysis set (see [Section 4.5](#)).

The primary objective of the study will be assessed using percent change in ER expression, however data will be summarised and analysed for the percent change and absolute change from baseline, and will also be analysed based on the log transformed values. This is to ensure comparability with the different methods of reporting used within the literature. For all summaries and analyses, baseline values equal to zero will be set to one and corresponding biopsy day ER expression value will be incremented by 1. The same will hold for the reporting of PgR expression. For listings, original values will be reported.

For percent change in ER, and PgR expression, if data permits, three separate analyses of covariance (ANCOVA) models will be fitted, one utilizing data from stage 1 and 2 only (5-7 days exposure), one utilizing data from stage 3 only (12-15 days exposure) and one utilizing data from all stages combined with on-treatment biomarker expression score as a dependent variable, baseline expression score as a covariate, and day of biopsy and treatment group as fixed effects.

An exploratory analysis utilizing data from all stages may also be performed with on-treatment biomarker expression score as a dependent variable, baseline expression score as a covariate, day of biopsy and treatment group as fixed effects and an interaction between day of biopsy and treatment group. Other covariates such as stage and country may be explored as well as interactions between covariates.

Least squares means (LS-means) estimates of the treatment effect will be calculated together with 80% CIs for all treatment durations (5 to 7 consecutive days of AZD9833 treatment for stage 1 and stage 2, and 12 to 15 consecutive days of AZD9833 treatment for stage 3), as per the model fitted. To calculate the percentage change, mean changes from baseline will be converted to percentage of initial staining by dividing mean changes by the overall mean score at baseline (Robertson et al 2013). The three ANCOVA models will be repeated based on the absolute change from baseline.

If the distribution of ER and PgR expressions manual H-score is normal, these data will be analysed as described previously and this will form the primary analysis. If data does not adequately follow a normal distribution, then the use of the natural log transformed data (i.e., ratio) will replace the untransformed analysis as the primary approach. Log transformed ANCOVA analyses will be produced including the same covariates as specified for the untransformed analyses, but with the log transformed baseline value replacing the untransformed value. The estimated treatment effect and its 80% CIs will be back transformed to the original scale prior to reporting. The values equal to zero (0) on the original scale will be set to 1, and corresponding baseline / biopsy day expressions scores will be incremented by 1 before natural log transformation.

The normality of the distribution of the data will be tested using a Shapiro-Wilk test. In case of a two-sided p-value > 0.20, there will be evidence that the data is normally distributed. Additional plots and

statistics will be provided to measure the severity of the deviations from normality if necessary. ***Sensitivity analyses for ER and PgR***

If necessary, the following sensitivity analysis will be conducted on a subset of the PD analysis set by excluding:

From ER analysis

- Any patients who are HER2 positive by central assessment.
- Any patients with an ER H-score < 10 on their pre-treatment biopsy.

From PgR analysis

- Any patients who are considered to be HER2 positive by central assessment.
- Any patients with a PgR H-score < 10 on their pre-treatment biopsy.

If considered necessary, further cuts and sensitivity analyses may be performed.

If following transformation of the data an ANCOVA model is still not appropriate, a non-parametric approach may be considered.

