4.2 General Data Presentation Characteristics

The data from all countries and stages will be combined and reported together. Stage 1 and Stage 2 data combined and Stage 3 data alone will also be reported separately. All data will be summarised by treatment group and timepoint.

Continuous data will be summarised using descriptive statistics (the number of patients [n], mean, standard deviation [SD], median, 25th and 75th percentiles [where appropriate], minimum and maximum unless otherwise stated). For log-transformed data it is more appropriate to present geometric mean (gmean), geometric coefficient of variation (CV), median, minimum and maximum.

For continuous data, the mean, median and gmean will be rounded to one additional decimal place compared to the original data. The SD and geometric CV will be rounded to two additional decimal places compared to the original data. Minimum and maximum will be displayed with the same accuracy as the original data. The maximum number of decimal places reported will be four for any summary statistic.

Categorical data will be summarised in terms of the number of patients providing data at the relevant time point (n), frequency counts and percentages. Percentages will not be presented for zero counts. Unless otherwise stated, percentages will be calculated using the number of patients included in the analysis set for that treatment group as denominator and presented to one decimal place.

Confidence intervals (CIs), when presented, will generally be constructed at the 2 sided 80% level. CIs will be presented to one additional decimal place compared to the original data.

For safety, PD, and PK endpoints the last observation prior to the first dose of study treatment will be considered the baseline measurement unless otherwise specified. For assessments on the day of first dose where time is not captured, a nominal pre-dose indicator, if available, will serve as evidence that the assessment occurred prior to first dose. Assessments on the day of first dose where neither time nor a nominal pre-dose indicator are captured will be considered prior to first dose if such procedures are required by the protocol to be conducted before first dose.

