Any information taken after first dose/administration of study medication will be regarded as post baseline information. If two visits are equally eligible to assess patient status at baseline (e.g., screening and baseline assessments both on the same date prior to first dose/administration), the average should be taken as the baseline value. For non-numeric laboratory tests (i.e. some of the urinalysis parameters) where taking an average is not possible then the best value will be taken as baseline as this is the most conservative. Where safety data are summarised over time, study day will be calculated in relation to date of first treatment. If no value exists before the first dose/administration, then the baseline value will be treated as missing.

In all summaries:

Change from baseline = post-baseline value - baseline value.

Percent change from baseline = (post-baseline value - baseline value)/baseline value × 100

For any variable subject to log transformation, the back transformed change from baseline, calculated and summarised on the log scale, will be presented as ‘baseline scaled ratio’ (BSR). Percentage change will then be calculated as (BSR – 1) x 100.

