4.10 Pharmacodynamic Evaluation

Biopsy samples will be sectioned and assessed for tumour content. Pathologist scoring for ER, PgR and Ki-67 expression will be carried out at a contracted external good clinical practice (GCP) accredited laboratory. Sections will be scored for ER, PgR and Ki-67 expression in tumour by a contracted independent pathologist who will be blinded to treatment groups.

For patients where more than one tumour block has been provided for a single timepoint, a weighted mean score based on the percentage (%) of tumour cells in each section will be used as the score for that timepoint. Non-invasive tumour biopsy scorings will be excluded from the PD summaries and listings.

For example: If $i=1, 2, 3 \dots n$ is the number of tumour blocks provided for a single patient for a particular tumour assessment visit; and the sample has corresponding percentage tumour tissues t_i and H-scores h_i (total H-score for ER and PgR expressions, and percentage tumour cells with positive nuclei for Ki-67 expression), then the weighted mean score for that patient for that particular visit is calculated as follows:

$$\sum_{i=1}^n \left(\frac{t_i}{\sum_{i=1}^n t_i} \right) h_i \quad \text{where } i=1,2, 3 \dots n$$

The weighted mean score will be used as is in the analyses, where the score will be rounded off to the nearest integer before presenting in the summary tables.

Pathology scoring will be summarised and listed by treatment group for all patients by Stage 1 and Stage 2 combined, Stage 3 alone, and by Stages 1, 2 and 3 combined by actual treatment group and by visit.

The receptor status will be listed for safety analysis set by ER and PgR total H-score, Ki67 labelling index, and HER2 IHC positive staining.

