4.10.2 Ki-67 Labelling Index

Ki-67 labelling index will be assessed and expressed as the average percentage of tumour cells with counted positive nuclei, following the International Ki-67 in Breast Cancer Working Group Recommendations. Ki-67 labelling index will be scored by increments of 1% and can range from 0 – 100. When the number of tumour cells per section for a counted biopsy is less than 100 tumour cells, then the Ki-67 labelling index is not reported and NE will be stated.

The secondary pharmacodynamic biomarker variables of change from baseline in Ki-67 labelling index after 5 to 7 days of AZD9833 treatment for Stage 1 and Stage 2; and after 12 to 15 days of AZD9833 treatment for Stage 3 will be listed and summarised based on the PD analysis set (see Section 4.5).

It is expected that the distribution of the Ki-67 labelling index data will not be normally distributed (Robertson et al 2013, Robertson et al 2020b), hence Ki-67 labelling index data will be naturally log-transformed before being analysed. Ki-67 will be analysed similarly to ER and PgR, using a parametric ANCOVA on natural log transformed data. Values equal to zero on the original scale will be set to one (1), and one will be added to the corresponding baseline/biopsy day labelling index value before natural log transformation. Log transformed baseline score will be included as a covariate, and day of biopsy and treatment group included as fixed effects. The estimated treatment effect together with 80% CIs for all treatment durations (5 to 7 consecutive days of AZD9833 treatment for stage 1 and stage 2, and 12 to 15 consecutive days of AZD9833 treatment for stage 3), as per the model fitted will be back transformed to the original scale for reporting. For listings, original values will be reported.

Sensitivity analyses for Ki-67 labelling index

If necessary, sensitivity analysis will be conducted on a subset of the PD analysis set by excluding:

- Any patients who are considered to be HER2 positive by central assessment.
- Any patients with a Ki-67 labelling index < 5% from their pre-treatment biopsy.
- Any patients with an ER H-score < 10 on their pre-treatment biopsy.
- Any patients with an ER H-score < 10 on their pre-treatment biopsy or any patients with a Ki-67 labelling index < 5% from their pre-treatment biopsy.

If considered necessary, further cuts and sensitivity analyses may be performed.

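### The zero rule fixes a baseline-zero patient's percent change at 100 times the on-treatment H-score, which distorts descriptive means (chiefly PgR), and the log-scale rule does not keep near-zero scores in order

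*SAP*

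**What the plan says.** SAP section 4.10.1 makes percent change in ER the measure for the primary objective. Absolute change and log-transformed values are also to be summarised and analysed. For every summary and analysis, "baseline values equal to zero will be set to one and corresponding biopsy day ER expression value will be incremented by 1", and "The same will hold for the reporting of PgR expression". The manual H-score is one "which yields to a manual H-score range of 0 to 300".

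Section 4.2 defines "Percent change from baseline = (post-baseline value - baseline value)/baseline value × 100" and says "Continuous data will be summarised using descriptive statistics", including mean, SD, median, minimum and maximum.

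For the log analyses, section 4.10.1 says "The values equal to zero (0) on the original scale will be set to 1, and corresponding baseline / biopsy day expressions scores" are raised by one. Section 4.10.2 does the same for Ki-67: "Values equal to zero on the original scale will be set to one (1), and one will be added to the corresponding" paired value. Pairs without a zero are left alone. Where several tumour blocks exist at one visit, section 4.10 forms a weighted mean for ER, PgR and Ki-67, and "The weighted mean score will be used as is in the analyses", so it enters unrounded.

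Two further provisions matter. The ANCOVA percentage in section 4.10.1 is a mean change divided by the overall baseline mean, not an average of patient percentages. Leaving out patients with a baseline ER or PgR H-score below 10 is a sensitivity analysis to be run only if judged necessary, with no trigger given.

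**The concern.** A percent change from a baseline of zero is undefined. The rule replaces it with a number that depends entirely on the constant chosen: under the same scheme a constant of 10 would give 10y instead of 100y. One such patient can dominate the mean and SD of a group of 12 to 36, and a reader of the descriptive table could not tell drug effect from artefact.

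The log rule raises a different problem. Because the shift is applied only when a zero is present, the transformation is not monotone near zero. Log ANCOVA is the planned Ki-67 analysis, and it becomes the primary approach for ER and PgR if the normality check fails. On-treatment scores at or near zero are plausible for a drug meant to suppress these markers.

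**Working it through.** **The plan's own precision figures (section 4.13), for scale.** Half-width = t(0.90, n-1) × 29 × √(χ²(0.80, n-1)/(n-1)) / √n. This gives 13.16 (n=12), 8.68 (n=24) and 6.90 (n=36), so the stated limits of 14, 9 and 7 hold. They concern ER with an SD of 29 and are not in dispute.

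**Percent change from a zero baseline.** Baseline 0 becomes 1 and on-treatment y becomes y+1:

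100 × ((y+1) - 1)/1 = 100y.

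So y=5 gives +500%, y=20 gives +2000% and y=300 gives +30000%.

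**Effect on a group mean.** Assumption: the other n-1 patients are all at -80%. The SAP gives no PgR effect and uses -80% only to illustrate Ki-67. Then mean = ((n-1)(-80) + 100y)/n and SD = (100y + 80)/√n. For n=24:

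| On-treatment y | Mean | SD | Median |
|---|---|---|---|
| 0 | (-1840 + 0)/24 = -76.7% | 80/4.899 = 16.3 | -80% |
| 5 | (-1840 + 500)/24 = -55.8% | 580/4.899 = 118 | -80% |
| 20 | (-1840 + 2000)/24 = +6.7% | 2080/4.899 = 425 | -80% |

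The mean turns positive when 100y exceeds 80(n-1), that is, for y above 8.8 (n=12), 18.4 (n=24) or 28.0 (n=36). With the others anywhere from -50% to -100%, the thresholds are 5.5 to 11, 11.5 to 23 and 17.5 to 35.

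**Effect on the other estimates.** Take n=24, the 23 others going 100 to 20 (assumed) and one patient going 0 to 20.
- Absolute change: (y+1) - 1 = y, the same as without the rule.
- Mean change over mean baseline, unadjusted: mean change = (-1840 + 20)/24 = -75.83. Mean baseline with the rule = 2301/24 = 95.88, giving -79.1%. Without the rule it is 2300/24 = 95.83, again -79.1%.
- Geometric mean ratio: exp[(23 ln 0.2 + ln 21)/24] = 0.243, or -75.7%.

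**Log rule, Ki-67 baseline 20.**

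| On-treatment | Value entering the log | Log | Ratio to baseline | Change |
|---|---|---|---|---|
| 0 | 1 (baseline becomes 21) | 0 | 1/21 | -95.2% |
| 0.5 | 0.5 | -0.69 | 0.5/20 | -97.5% |
| 1 | 1 | 0 | 1/20 | -95.0% |

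A mean of 0.5 arises from two blocks of equal tumour content scored 0 and 1. With whole-number scores at the same baseline the ratio keeps its order, but 0 and 1 tie in the dependent variable. Between different baselines whole numbers are enough for a reversal: 50 to 0 gives 1/51 - 1 = -98.0%, while 100 to 1 gives -99.0%.

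**One constant for every score (1 added throughout), baseline 20.** 0 gives 1/21 = -95.2%, 0.5 gives 1.5/21 = -92.9% and 1 gives 2/21 = -90.5%. Order is restored at equal baseline. It is not restored across baselines: 20 to 0 gives -95.2%, while 100 to 1 gives 2/101 - 1 = -98.0%.

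**The case against.** The strongest reply concerns reach, and most of it stands.

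- **Model-based results.** A reader might infer that the main estimate of ER or PgR change could reverse sign. The SAP does not support that. Its ANCOVA percentage divides a mean change by the overall baseline mean, and the check above shows it unmoved. The log analysis and the median do not reverse either.
- **ER.** A reader might extend the harm to ER because baseline scores below 10 are foreseen. The rule acts only at exactly 0, and section 1 enrols ER-positive tumours, so ER should rarely be touched.
- **Cause.** Small denominators inflate per-patient percentages without any zero rule: 1 to 21 is also +2000%. This is correct, and it is why the median must be read with the mean. It does not justify inventing a value at zero.
- **Likelihood.** The reversal needs a PgR score that rises from 0 on treatment. The SAP gives no frequency for zero baselines or for such rises. If the score stays at 0, the mean moves only from -80% to -76.7%.
- **Log scale.** A reader might conclude that complete suppression is generally scored as less than near-complete suppression. At equal baseline that needs a fractional multi-block mean. Ki-67 is scored in 1% steps, so single-block values only tie.
- **Existing safeguards.** The median, the absolute change and listings of original values are already planned. The exclusion below 10 is listed, but nothing obliges anyone to run it.

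**Conclusion.** The point holds within limits. As written, the zero rule gives a baseline-zero patient a percent change of exactly 100y. This can inflate, and in small groups reverse, the descriptive arithmetic mean of per-patient percent change, and it inflates the SD and maximum, chiefly for PgR, a secondary endpoint. The sizes shown rest on two assumptions: the other patients at -80%, and one patient whose score rises from zero. The primary ER analysis is not threatened.

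The log rule is a separate, smaller defect: it ties 0 with 1 in the dependent variable and ranks an unrounded 0.5 below a true zero. In the Ki-67 example the difference is -95.2% against -97.5%.

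Severity is moderate. The results are artefacts of stated rules and easy to remove, but this is an exploratory estimation study and the model-based estimates are largely protected.

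**What to change.** 1. **Per-patient percent change in ER and PgR.** Drop the set-to-one rule. Report percent change as not calculable when baseline is 0, show how many patients this removes in each group, and present the mean together with the planned median. Keep all patients, with original scores, in the absolute-change summaries and the untransformed ANCOVA. Keep the exclusion of baseline scores below 10 as a sensitivity analysis, but run it whenever such patients exist. Making it the main mean would be a trade-off, because it also removes scores of 1 to 9 that the zero rule never touches.
2. **Log analyses of ER, PgR and Ki-67.** Add one constant, for example 1, to every score of every patient at both visits, with one alternative constant as a sensitivity analysis. This restores order at equal baseline, though not between different baselines.

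The cost is SAP wording and derivation code. A few patients leave the percent-change summary, and reductions at very low scores shrink slightly. The change should be settled before database lock, because the study is open-label and a zero rule chosen once the zeros are known would be data-driven.

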1 INTRODUCTION

This is a randomised, open-label, parallel-group, multicentre study which has three stages to help investigating the biological effects of different doses of AZD9833 orally administered (PO) once daily (QD), in women with primary breast cancer awaiting curative-intent surgery, for 5 to 7 days consecutively in Stage 1 and 2; for 12 to 15 days consecutively in Stage 3. Women with histologically proven, oestrogen receptor-positive (ER-positive), human epidermal growth receptor 2-negative (HER2-negative) invasive breast cancer involving a palpable tumour of any size, or a tumour with an ultrasound assessed diameter ≥ 1.0 cm and fulfilling all the inclusion criteria and none of the exclusion criteria will be enrolled in the study.

In Stage 1, approximately twenty-four evaluable post-menopausal women will be randomly assigned in a 1:1 ratio to two dose groups (75 mg PO QD for 5 to 7 days and 150 mg PO QD for 5 to 7 days) of AZD9833. Following completion of Stage 1 and availability of immunohistochemistry (IHC) data, the Safety and Data Monitoring Committee (SDMC) will review the Stage 1 data, potentially alongside the emerging data from any relevant ongoing AZD9833 studies and decide whether to proceed with Stage 2 based on the guidelines provided in the SDMC charter.

Following the review of the Stage 1 data, the SDMC has advised that Stage 2 will comprise of approximately thirty-six evaluable post-menopausal women from Georgia (GE) and Mexico (MX), randomly assigned in a 1:1:1 ratio to three dose groups (75 mg PO QD for 5 to 7 days, 150 mg PO QD for 5 to 7 days and 300 mg PO QD for 5 to 7 days) of AZD9833 and approximately twenty-four post-menopausal women from the United Kingdom (UK) randomly assigned in a 1:1 ratio to two AZD9833 dose groups (75 mg PO QD for 5 to 7 days and 150 mg PO QD for 5 to 7 days).

Following the interim analysis after Georgia and Mexico completed recruitment in Stages 1 and 2, the SDMC has advised that Stage 3 of the study should be conducted to include forty-eight evaluable post-menopausal women from Georgia (GE) and Mexico (MX), randomly assigned in a 1:1 ratio to two AZD9833 dose groups (75 mg PO QD for 12 to 15 days, 150 mg PO QD for 12 to 15).

This statistical analysis plan (SAP) provides the technical elaboration of the statistical analysis of pharmacodynamic (PD), safety and pharmacokinetic (PK) data.

The analyses described in this SAP are based upon the following study documents:

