3 INVESTIGATIONAL PLAN

3.1 Stage 1

After the screening visit and confirmation of eligibility, patients will be randomly assigned in a 1:1 ratio to receive one of the following two treatments for 5 to 7 days:

Group 1: AZD9833 75 mg once daily (n = 12 evaluable post-menopausal patients)

Group 2: AZD9833 150 mg once daily (n = 12 evaluable post-menopausal patients)

During the treatment period the patients will attend visits on:

Day 1

[figure not shown]
Day 5, 6 or 7 for an on-treatment imaging-guided biopsy

Day of surgery (following a washout period of at least 5 days after taking the last dose of AZD9833 on Day 5, 6 or 7, the patients will undergo curative-intent surgery i.e. study day \geq 11)

28 day safety follow-up (after last dose of the study treatment for AZD9833)

The general study design of Stage 1 is summarised in [Figure 1](#)

Figure 1 : Study Design Stage 1

3.2 Stage 2

After the screening visit (up to 21 days prior to randomisation) and confirmation of eligibility, patients will be randomly assigned in a 1:1 or 1:1:1 ratio to receive one of the following two or three treatments (based on the geographical stratification factor) for 5 to 7 days:

- Group 1: AZD9833 (75 mg, PO, once daily for 5 to 7 days; approximately 24 evaluable patients [12 UK])
- Group 2: AZD9833 (150 mg, PO, once daily for 5 to 7 days; approximately 24 evaluable patients [12 UK])
- Group 3: AZD9833 (300 mg, PO, once daily for 5 to 7 days; approximately 12 evaluable patients)

[figure not shown]
During the treatment period, patients will attend study visits on:

- Day 1
- Day of biopsy (Day 5, 6 or 7)
- Day of surgery (following a washout from AZD9833 for at least 5 days; ie if AZD9833 was taken for the last time on morning of Day 5, then Days 6, 7, 8, 9 and 10 are washout days and surgery can be scheduled for Day 11 onwards). In the event that a patient is undergoing longer-term neoadjuvant therapy rather than surgery, the ‘surgery day’ visit should be conducted on Day 13 (+ 3 days)
- 28 day safety follow-up (after last dose of the study treatment for AZD9833)

A treatment window of 5 to 7 days, along with a washout period of 5 days is considered to permit curative intent surgery within existing standard of care timeframes.

The general study design of Stage 2 is summarised in [Figure 2](#).

Figure 2: Study Design Stage 2

3.3 Stage 3

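### The Stage 1+2 and all-stages ANCOVAs omit geography, which decides access to 300 mg, so one third of any regional difference enters the 300 mg and duration comparisons

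*SAP*

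**What the plan says.** SAP Section 4.10.1 commits to three ANCOVAs for ER and for PgR: Stages 1 and 2 together, Stage 3 alone, and all stages. Each takes the on-treatment score as outcome, with "baseline expression score as a covariate, and day of biopsy and treatment group as fixed effects". Section 4.10.2 does the same for Ki-67 on the log scale: "Log transformed baseline score will be included as a covariate, and day of biopsy and treatment group included as fixed effects".

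Stage 2 allocation depends on where the patient is enrolled. Section 3.2 says patients are randomised to "one of the following two or three treatments (based on the geographical stratification factor) for 5 to 7 days". Section 1 gives the detail: Georgia/Mexico (GE/MX) patients are "randomly assigned in a 1:1:1 ratio to three dose groups" (75, 150 and 300 mg), while the UK contributes "approximately twenty-four post-menopausal women from the United Kingdom (UK) randomly assigned in a 1:1 ratio to two AZD9833 dose groups" (75 and 150 mg). Stage 3 enrols in GE/MX only.

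Geography and stage enter the modelling only as an option, attached to an all-stages analysis that is itself optional: "Other covariates such as stage and country may be explored as well as interactions between covariates". Section 4.16 adds a selection of summaries split into GE/MX and UK. Section 4.13 says the UK patients are recruited to learn whether dose-response is the same in the two geographies.

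**The concern.** Leaving a stratification factor out of a model usually costs only precision, because each stratum has the same allocation ratio. Here the ratios differ: the chance of receiving 300 mg is one in three for a Stage 2 GE/MX patient and zero for a UK patient. Pooling regions without a region term therefore compares a 300 mg group drawn from one region with 75 and 150 mg groups drawn from two. The all-stages model has a parallel problem: days 12-15 come from GE/MX alone, while days 5-7 include UK patients.

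If response differs by region, for example through case mix or biopsy handling, part of that difference would appear as an effect of 300 mg or of longer treatment. The confidence interval would not reflect it, and more patients in the same proportions would not remove it. The SAP treats homogeneity across geographies as an open question in Section 4.13, yet its committed models assume it.

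**Working it through.** **1. The SAP's own precision figures.** Section 4.13 assumes SD 29 and two-sided 80% intervals. With half-width = t(0.90, n−1) × 29 × √[χ²(0.80, n−1)/(n−1)] / √n, the results are 13.16, 8.68 and 6.90 for n = 12, 24 and 36. Rounded up, these match the stated 14, 9 and 7, so SD 29 is used below.

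**2. Planned composition** (Sections 1, 3.1 to 3.3 and Table 1). Table 1 counts about 60 GE/MX patients over Stages 1 and 2. Stage 2 supplies 36 of them, and 60 − 36 = 24 is the whole of Stage 1. That Stage 1 was entirely GE/MX is therefore inferred from approximate figures, not stated.

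| Dose | Stage 1 GE/MX | Stage 2 GE/MX | Stage 2 UK | UK share, Stages 1+2 | Stage 3 GE/MX |
|---|---|---|---|---|---|
| 75 mg | 12 | 12 | 12 | 12/36 | 24 |
| 150 mg | 12 | 12 | 12 | 12/36 | 24 |
| 300 mg | 0 | 12 | 0 | 0/12 | 0 |

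**3. Bias from omitting region.** Let Δ be the UK minus GE/MX difference in baseline-adjusted response. Assume biopsy days are spread evenly within each cell.

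- 300 minus 75 (or 150) mg: (0/12 − 12/36) × Δ = −0.33Δ. Projecting a UK indicator on the dose and day terms gives the same coefficient in the Stage 1+2 and all-stages models.
- Days 12-15 minus days 5-7, all-stages model: (0/24 − 12/36) × Δ = −0.33Δ at 75 and 150 mg.
- 150 minus 75 mg: (12/36 − 12/36) × Δ = 0 in Stages 1+2, and likewise 12/60 − 12/60 = 0 over all stages.
- Stage 3-only model: one region, so no bias.

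The 300 mg group also has no Stage 1 patients, against 12/36 at the other doses. The same one third therefore applies to any Stage 1 minus Stage 2 difference.

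**4. Size.** The SAP gives no value for Δ. Assumed values of 5, 10 and 20 points give 5/3 = 1.7, 10/3 = 3.3 and 20/3 = 6.7 points. For 300 versus 75 mg, SE = 29 × √(1/36 + 1/12) = 29/3 = 9.67, and the 80% half-width is t(0.90, 46) × 9.67 ≈ 12.6 (12.4 with the normal quantile). For Ki-67, one third of the regional difference on the log scale carries over in the same way.

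**5. Cost of adjustment in the Stage 1+2 model** (SD 29, baseline covariate left aside).

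- Region added: Δ is estimated from the 75 and 150 mg groups with variance σ²(1/24 + 1/12)/2 = 0.0625σ². The variance of 300 versus 75 mg is σ²(1/12 + 1/36 + 0.0625/9) = 0.1181σ², so SE = 9.96, up 3% from 9.67.
- Region and a Stage 1/2 indicator added: σ²(1/12 + 1/36 + 1/36) = 0.1389σ², so SE = 10.81, up 12%.
- 150 versus 75 mg: SE stays at 6.84 throughout.

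In the all-stages model, adding region moves the 300 versus 75 mg SE from 9.42 to 9.73.

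**6. Duration and stage.** Days 12-15 occur only in Stage 3. Adding stage to the all-stages model that already has region and day of biopsy gives 12 columns of rank 11, so duration and Stage 3 cannot be separated.

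**The case against.** The strongest reply is that the study is exploratory estimation. It is sized on the change within each dose group, and it reports LS-means with 80% intervals. Section 4.10.1 specifies no 300 versus 75 mg contrast, no duration contrast and no hypothesis test between doses. That stands: the point concerns how adjusted means in one table are read against each other, and no type I error is at stake.

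It can also be said that the SAP leaves room for geography: the optional covariates, the split summaries in Section 4.16, and a possible UK-specific interim in the footnote to Table 1. These provisions are optional or descriptive, and none commits the Stage 1+2 model to a region term. Because Section 3.5 has the sponsor's and contractor's teams unblinded throughout, a covariate chosen later could be chosen on the results.

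The one-third share belongs to the completed Stages 1+2. The Stage 2 interim was triggered by GE/MX completion and took only whatever UK data were available, so the UK share there may have been smaller.

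A reader might infer that all the dose comparisons are confounded. The planned numbers do not support this: 75 and 150 mg are allocated 1:1 in every stage and region. A reader might also set the shift against the 7-point half-width in Section 4.13, but that figure describes one 36-patient mean, not a contrast with a 12-patient group.

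**Conclusion.** The point holds for the 300 mg comparisons in the Stage 1+2 and all-stages models and for the duration comparison in the all-stages model. One third of any regional difference enters each. The shift would be about 1.7 to 6.7 points if the regional difference were 5 to 20 points, which is at most about half of the 12.6-point half-width for 300 versus 75 mg. This rests on the planned counts, on Stage 1 being all GE/MX (inferred), on evenly spread biopsy days, and on an assumed regional difference.

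Two further inferences should be resisted. The confounding of 300 mg with region is partial, since two thirds of the 75 and 150 mg patients are also GE/MX. And a region term does not by itself make 300 mg a fully randomised comparison, because the Stage 1 patients are not concurrent, nor can any covariate separate duration from Stage 3.

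Severity: should-fix. The correction is nearly free, but in an exploratory estimation study with no specified between-dose test the omission does not invalidate the main results.

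**What to change.** - In Sections 4.10.1 and 4.10.2, prespecify geography (GE/MX versus UK) as a fixed effect in the Stage 1+2 and all-stages ANCOVAs for ER, PgR and Ki-67, with LS-means at observed margins. State that the adjusted 300 mg mean assumes the regional difference is the same at every dose, since no UK patient receives 300 mg.
- As a sensitivity analysis, either report 300 mg against 75 and 150 mg among the concurrently randomised Stage 2 GE/MX patients, or add a Stage 1/2 indicator to the Stage 1+2 model (SE 10.81). The first option has about 12 per arm: 29 × √(2/12) = 11.84, giving an 80% half-width of about 15 to 16.
- Label any comparison of 5-7 with 12-15 days as non-randomised, including within GE/MX, because duration is wholly aliased with Stage 3.

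The cost is SAP wording and one model term: one degree of freedom, about 3% on the 300 versus 75 mg SE, and nothing on 150 versus 75 mg. No new data are needed, because Section 4.6.1 already tabulates patients by country.
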